4.17 Sample Size and Power

Our analysis of pilot data demonstrates a 48% difference in ICS adherence when comparing a time interval with financial incentives (the same schema proposed in this study) to a time period without incentives. To ensure a power of 80% at a significance level of 0.05 to detect a more conservative 30% difference in average adherence between arms 1 and 3 in the *Experiment* phase (corresponding to 65% and 35%, respectively), 40 patients are required in each of these two arms. To ensure scientific rigor given the vulnerable nature of the population, we estimate ~20% loss to follow-up. Therefore, we will aim to enroll 50 participants in study arms 1 and 3 and 25 participants in arm 2, or 125 participants total, to achieve sufficient power to detect a difference between arms 1 and 3. The study is not to be powered to detect differences in arms 1 to 2 or 2 to 3 (hence the 2:1:2 randomization schema) or for health outcomes or cost offset; rather, it is intended to obtain preliminary estimates of marginal effects of the intervention components and effect sizes on utilization outcomes by comparing arm 1 to 2 and 2 to 3 to power a future multicenter study. Baseline data reveals that ~50% of children with at least 2 prior hospitalizations have a repeat ED visit or inpatient stay 6 months after the 2nd hospital discharge.

4.18 Additional analyses

Hypothesis 1.2 Longer time intervals to next asthma-related ED or inpatient visit, and reduced healthcare use and costs, will be observed in Arm 1 compared to Arms 2 and 3 (and in Arm 2 compared to Arm 3).

Time to next asthma-related ED or inpatient visit from enrollment will be first modeled using the Kaplan-Meier plots. Study arms will be compared using log-rank tests and unadjusted Cox proportion hazards models. Adjusted hazard models will include the additional covariates described above and the Anderson-Gill method will be used to account for recurrent events. Total medical costs will be estimated for the 12 months following study enrollment, accounting for each asthma-related ED visit and hospitalization, as well as the expenses incurred with study participant incentives, sensors, and use of the WTH automated platform. We predict that intervention will reduce medical costs, thereby contributing to a *cost offset*. We will estimate potential savings in medical costs by calculating the difference in average total medical costs minus study-related expenses between study arms.

Aim 2. Assess proposed mechanisms by which intervention strategy influenced adherence trajectory.

Aim overview: The broad goal of this aim is to assess which participant and study characteristics are associated with different longitudinal adherence trajectories.

Characteristics to be examined include baseline factors (demographic, clinical, and prior health utilization factors), intervention strategy (study arm), and potentially modifiable behavioral characteristics. Of specific interest is how intervention strategy in the Experiment phase (study arm) influences child asthma self-efficacy, shared medication responsibility, and medication habit over time and how these characteristics vary with longitudinal ICS adherence trajectories. [Figure 4]

Hypothesis 2: Increases in (1) participant self-efficacy, (2) shared medication responsibility, and (3) habit score will partially mediate the relationship between study arm and sustained adherence trajectory.

ICS adherence trajectories will be characterized using group-based trajectory modeling (GBTM). GBTM is an analytic technique used to identify and characterize differential patterns of changing behavior over time in a population of interest. In GBTM, an individual is assumed to belong to only one group, of which each group has its own trajectory. I will specify several models with different number of groups (e.g. 2 to 5) using quadratic trajectories (or possibly higher order polynomials) and compare these models to identify the one that best fits our ICS use data based on both the Bayesian information criterion and group percentages that are sufficiently large (e.g. >5% of the entire sample) to ensure study power as well as model stability. The group-based trajectory modeling will be performed using PROC TRAJ macro implemented in SAS (SAS 9.3).

Once adherence trajectory groups have been determined, I will first use bivariate multinomial or ordered logistic regression models to estimate odds ratios (ORs) for the three predictors of interest, as well as baseline demographic, clinical, and health utilization characteristics, on trajectory group membership. When applying the ordered logistic regression, I will check the proportional odds assumption using the Brant test. All variables that are not marginally predictive of any trajectory group in bivariate analyses ($P\text{-value} > 0.2$) will not be included in the multivariable analysis. I will then construct a final multivariable multinomial regression model of trajectory of all marginally predictive covariates, first including (1) baseline demographic and clinical characteristics, then (2) study arm, and lastly, (3) the three hypothesized potential mechanisms.⁷ Mediation analysis will be conducted with variables associated with both study arm and trajectory membership. Covariance matrices will be generated and regression estimates standardized to obtain an overall mediated effect of each potential mechanism variable (e.g. child self-efficacy) on each study arm. The percentage of the total effect of study arm that is mediated by child self-efficacy, for instance, will be calculated using standardized beta estimates.⁸ If self-efficacy, shared responsibility, and habit index are not associated with study arm or adherence trajectory, I will then assess the additional behavioral constructs described in the “Covariates” section (medication beliefs,

[figure not shown]

Figure 4: Potential mechanisms for study arm effect on adherence trajectory

descriptive and injunctive norms, and current asthma symptom burden) as potential alternative mediators.

Aim 3. Explore caregiver and child perceptions of acceptability of intervention components and how they influenced adherence trajectory.

Aim overview: The final aim will use data from the semi-structured interviews conducted at the 6-month visit in a randomly selected subset of study participants to gain in-depth insight into the family and child experience of the intervention components with particular attention to perceived influence, or lack of influence, of the ICS adherence incentives on adherence behavior. In addition, we will explore other factors children and caregivers perceived as influencing their daily ICS adherence. Interview prompts will include the perceived impact of the intervention components (financial incentives, adherence reminders, adherence feedback, study app, electronic monitoring), component design factors (duration of incentive exposure, duration and frequency of reminders and feedback, child and caregiver engagement strategies, and potential alternative incentive strategies), and non-intervention factors (medication access, perceived medication efficacy, and family and social circumstances). Using the trajectory groupings derived from the prior aims, we will then assess whether themes differ between families of children with different daily use trajectories.

Semi-structured interviews will be audio-recorded. Audio files will be transcribed verbatim. Field notes and interview transcripts will be uploaded to NVivo 12 software. Co-mentor [name] will help train a research assistant to assist in the coding of data. We will use inductive theory-building⁹ and the constant comparative method¹⁰ to identify data patterns. We will first read through all documents using open coding to record salient themes that emerge that will be further refined during axial coding in a second stage. At this stage, we will begin to generate explanations for emerging patterns in the data. After generating a draft code list, we will review interview transcripts and our field notes to determine which codes fit the concepts suggested by the data. As we discover themes and patterns, we will consistently search for negative cases within the data to refine our analysis.¹¹ Coding discrepancies will be logged and discussed by myself, co-mentor [name], and the research assistant to examine reasons for the discrepancy, to inform theory and interpretation of the data, and refine analytic procedures.

We will then use trajectory group membership from the prior aims to categorize participants into sustained ICS versus non-sustained trajectory and explore the ways in which perceived intervention effects and experiences differ between these groups. If the distribution allows, we will attempt further categorization of the non-sustained group into specific trajectory grouping (i.e. severe early non-adherence, intermittent adherence, etc).

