1.4 Relevant Literature and Data

Improving adherence, particularly in high-risk populations, is challenging. Previous interventions to improve medication adherence have demonstrated effects that are modest, at best^{6,7}; thus, several emerging areas of study have catalyzed reinvestment in adherence interventions. First, technology-enhanced reminder systems have demonstrated robust ICS adherence improvements in other countries.⁸⁻¹⁰ Second, adult interventions infused with financial and social incentives from behavioral economics have enhanced behaviors as varied as medication adherence to smoking cessation.^{11,12} Few studies, however, have attempted to leverage mobile health technology and incentive design to improve medication adherence in children with high-risk asthma.

Two critical challenges limit the effectiveness of existing adherence interventions: (1) lack of knowledge of what it takes to engage high risk children and their caregivers, and (2) lack of enduring behavior change beyond the active intervention phase. Recent studies have begun to identify intervention components that tend to be more effective in engaging minority demographic groups¹³ and lead to sustained behavior change or habit formation.¹⁴ We recently conducted a pilot study of daily adherence reminders and feedback enriched with nominal financial adherence incentives (\$1/day for 30 days for perfect adherence) in families of children ages 5-11 with 3 asthma hospitalizations in the prior year. Study enrollment (69%) and mean ICS adherence (80%) during the intervention month were robust; however, adherence dropped to 33% after incentives, reminders, and feedback ceased. These findings reveal that financial incentives are a compelling method to engage this high-risk asthma population in regular ICS use, but whether and how adherence can be maintained and lead to sustained high adherence trajectories is unknown in pediatric populations.

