3.1.3 Experiment Phase (Months 1-3) and Observation Phase (Months 4-6)

The three experimental conditions will be: financial incentives, adherence reminders, and feedback (Arm 1); adherence reminders and feedback without incentives (Arm 2); or electronic monitoring alone (Arm 3). The financial incentives in Arm 1 will consist of 3 months of fixed-ratio incentives for each ICS actuation (i.e. 25 cents per puff for children on 4 daily ICS doses and 50 cents per puff for children on 2 daily doses), with a maximum of \$1 per day. With regard to the reminders and feedback in Arms 1 and 2, study participants will receive automated daily text message or push notification reminders and automated weekly feedback summarizing their adherence performance through Way to Health, a mobile health, electronic monitoring platform (described below in section 4.1). At the end of the first month of the experiment phase, families will be contacted by study staff to complete a follow-up survey that will reassess disease control, medication supply, and intentions and behaviors with

regard to ICS use (study visit 2). After the experiment interval, families will be contacted again by study staff to complete a follow-up survey and a semi-structured interview (study visit 3). At this point, all reminders, feedback, and incentives will cease, but daily ICS use monitoring will continue with the electronic sensors for all study arms (*Observation* phase) to assess for enduring effects. There will be a fourth study visit in the 7th study month, when study surveys will be completed, and a fifth and final study visit at one year assessing asthma control and health care utilization outside of the CHOP system.

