4.11 Screening and Monitoring Evaluations and Measurements

4.11.1 Medical Record Review

Variables to be abstracted from the medical chart:

- Child sex
- Date of birth
- Weight and height
- Date of qualifying hospital admission and discharge
- Asthma severity
- Last spirometry result and date of assessment (if reported)
- Name and dose of current asthma medications (both controllers and rescue)
- Number of prescriptions and refills in the prior year for each asthma medication
- Number and date of ED visits, hospitalizations, and oral steroid courses for asthma in the preceding year
- Number and date of ED visits, hospitalizations, and oral steroid courses for asthma during the 13-month study period

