4.16.2 Efficacy Analysis

We will assess the effectiveness of randomization by comparing the study arm balance on key demographic, clinical, and past health care utilization variables using analysis of variance (ANOVA) and t-tests or the nonparametric equivalent for continuous variables and chi-square tests or Fisher exact tests for categorical variables.

Primary analysis: Our primary outcome will be monthly ICS adherence in months 0-3 (Experiment Phase). Secondary outcomes will include monthly ICS adherence in months 4-6 (Observation Phase), asthma control at the end of the Experiment and Observation period. Secondary outcomes will also include monthly ICS adherence in months 7-13 (follow up period) to assess feasibility and acceptability of longer durations of electronic monitoring. We will consider arcsine transformation on the ICS adherence outcomes as necessary. This technique is commonly used for proportion data. We will use generalized estimating equations (GEE) to adjust for within-subject correlations due to repeated measures for the study's primary and secondary monthly adherence outcomes. Models will include main effects for arm and time (month) and arm-by-month interaction terms to allow for differing ICS adherence over time between arms. The dependent variable of monthly ICS adherence will be defined as mean daily observed-to-prescribed ICS actuation proportion for each study month. Mean daily adherence proportion will be capped at 1, such that participants taking more than their prescribed daily dose cannot receive "extra credit" for doses taken on those days. All statistical tests will be 2-sided. A P-value <0.05 will be considered statistically significant.

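### Section 4.18 plans one whole-period hazard ratio, timed from enrollment, for a three-month intervention; it cannot tell a transient effect on ED and inpatient visits from a smaller lasting one

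*Combined protocol and SAP*

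**What the plan says.** Section 4.18 (Hypothesis 1.2) measures time to the next asthma-related ED or inpatient visit from enrollment, starting with Kaplan-Meier plots. It then states: "Study arms will be compared using log-rank tests and unadjusted Cox proportion hazards models". Covariate-adjusted models follow, with the Andersen-Gill method for recurrent events. The section gives no end of follow-up for these models, no arm-by-time or arm-by-phase term, and no check of proportional hazards.

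Other sections fix the timing:

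- Section 3.1.3 gives Arm 1 "3 months of fixed-ratio incentives for each ICS actuation". Reminders and feedback in Arms 1 and 2 run over the same three months, and everything stops at the end of the Experiment phase. Monitoring continues so that lasting effects can be looked for.
- Sections 3.1.2 and 3.2 place randomization at the end of a four-week run-in that begins on the day of enrollment (3.1.1).
- Section 4.11.1 abstracts "Number and date of ED visits, hospitalizations, and oral steroid courses for asthma during the 13-month study period". The cost analysis in 4.18 covers 12 months from enrollment.
- Section 4.16.2 treats adherence differently. It separates the phases and fits arm-by-month interactions.
- Section 4.17 says that the trial is not powered for health outcomes, but that it should yield utilization effect sizes to help power a multicenter study.

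**The concern.** A single hazard ratio describes the arms well if they differ by a roughly constant factor. Here the difference in treatment occupies 3 of about 13 months. There is also a specific reason to expect fading: in the pilot described in section 1.4, mean adherence was 80% during the intervention month, and "adherence dropped to 33% after incentives, reminders, and feedback ceased". If visits follow adherence, the reported ratio averages an on-treatment effect with months in which the arms are treated alike, and its value depends on how long follow-up runs.

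The enrollment clock adds a separate dilution. During the run-in no child has yet been assigned, so that month pulls the ratio toward 1 even when the effect lasts.

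What is at stake is interpretation rather than significance. A future trial would be designed differently for a strong effect that lasts as long as the incentives than for a modest effect that endures. One overall ratio is compatible with both.

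**Working it through.** **The plan's own figure.** No event count, hazard ratio or power is given for Hypothesis 1.2. The only sample-size figure is for adherence. Section 4.17 sets it out: "To ensure a power of 80% at a significance level of 0.05", "corresponding to 65% and 35%, respectively), 40 patients are required in each of these two arms". With two proportions and unpooled variance, n = (1.96 + 0.8416)² × (2 × 0.65 × 0.35) / 0.30² = 7.849 × 0.455 / 0.09 = 39.7, so 40 per arm. Dividing by 0.8 for 20% loss gives 50. The figure reproduces, and it supplies the 50 versus 50 used below.

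**Inputs for the check**

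- Control event rate: about 50% by six months (4.17). A constant hazard is assumed, λ = ln 2 / 6 = 0.1155 per month. The 50% describes children with at least two prior hospitalizations, and eligibility is broader, so 30% is also shown.
- Clock from enrollment: run-in 0–1, Experiment 1–4, Observation 4–7, follow-up 7–13 months.
- On-treatment hazard ratio h: not in the documents. Assumed to be 0.6, with 0.5 to 0.7 as the range.
- No carry-over: ratio 1 outside months 1–4. No loss to follow-up.

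**Formulas.** With event densities f₀ and f₁ and survival functions S₀ and S₁ in Arms 3 and 1, the large-sample Cox log hazard ratio b solves ∫ { f₁ − (f₀ + f₁) · S₁eᵇ / (S₁eᵇ + S₀) } dt = 0. The Andersen-Gill rate ratio is the time average of the hazard ratio, (10 + 3h)/13 over 13 months.

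| On-treatment HR | Cox, enrollment to month 7 | Cox, to month 12 | Cox, to month 13 | Andersen-Gill, to month 13 |
|---|---|---|---|---|
| 0.5 | 0.77 | 0.83 | 0.84 | 11.5/13 = 0.88 |
| 0.6 | 0.81 | 0.86 | 0.87 | 11.8/13 = 0.91 |
| 0.7 | 0.86 | 0.90 | 0.90 | 12.1/13 = 0.93 |

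With a 30% six-month rate, the 13-month Cox values are 0.86, 0.89 and 0.91.

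**If the effect lasts.** With h = 0.6 from month 1 to month 13, the enrollment-clock Cox ratio is 0.65, and the Andersen-Gill ratio is (1 + 12 × 0.6)/13 = 0.63. Started at randomization, the same equation returns exactly 0.60, so the gap comes entirely from the run-in month. If half of the log effect carries through Observation and none after it, the Cox ratio is 0.74 at month 7 and 0.82 at month 13.

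**Two different truths, one number.** A transient 0.60 gives 0.868 at 13 months. A lasting 0.85 from randomization onward, put through the same equation, gives 0.870.

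**Precision of a phase-specific estimate.** For h = 0.5 on a randomization clock, expected first events in the Experiment phase are 50 × (1 − e^(−3λ)) = 50 × 0.293 = 14.6 in Arm 3 and 50 × (1 − e^(−1.5λ)) = 50 × 0.159 = 8.0 in Arm 1, together 22.6. On the enrollment clock both are multiplied by e^(−λ) = 0.891, giving 20.1. The standard error of the log ratio is about √(1/8.0 + 1/14.6) = 0.44, so the 95% interval around 0.50 is roughly 0.21 to 1.18. For Arm 1 versus Arm 2, if Arm 2 has the control hazard, there are about 8.0 and 7.3 events and the interval is roughly 0.18 to 1.36.

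Log-rank power at h = 0.6 is about 23% for the Experiment phase alone, 9% from enrollment to 13 months with no carry-over, and 43% over that window if the effect persists.

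**The case against.** The strongest reply is that the whole-period comparison is a legitimate estimand. It answers the hypothesis as worded, matches the 12-month cost window, and suits a trial that asks whether effects endure. The log-rank test remains valid under the null without proportional hazards. If the effect does persist, the longer window gains power. All of this stands, and it is why the whole-period comparison should stay.

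Several stronger readings are tempting, but the documents do not support them:

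- A reader might infer that any real effect will be diluted by untreated months. Only an effect that fades is diluted in that way; a persistent one loses only the run-in month.
- A reader might infer that the trial's own data contradict proportional hazards. The pilot was a separate study that paid incentives for 30 days to children with three hospitalizations, and it reported adherence rather than visits. It makes a waning effect plausible and does not establish it.
- A reader might take 13 months as the stated analysis window. It is the abstraction period; the survival analysis has no stated end.
- A reader might see a contradiction in 4.18 omitting oral steroid courses, which 4.15 lists. A count of courses and a time to ED or inpatient visit are different endpoints.

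One might also say that enrollment in 4.18 means randomization, since 3.3.2 reports enrollment to the funder that way and one sentence of 7.1.1 speaks of assignment at enrollment. The rest of 7.1.1, with 3.1.1, 3.1.2 and 3.2, separates the two dates. Even on a randomization clock over 12 months, the no-carry-over Cox ratios are 0.81, 0.85 and 0.89.

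The planned Kaplan-Meier curves would show the timing of any separation, but they give no estimate to carry forward.

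**Conclusion.** The point holds as a gap in specification and interpretability. Section 4.18 plans one time-constant arm effect on a clock that starts before assignment, with no censoring time and no phase-specific estimate. Under full washout, on-treatment ratios of 0.5 to 0.7 would be reported as about 0.84 to 0.90 (Andersen-Gill 0.88 to 0.93). Under full persistence of 0.6, the report would be about 0.65.

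These sizes rest on an assumed on-treatment effect, a constant control hazard at the stated 50% six-month rate, and an inferred 13-month window. They illustrate sensitivity and do not predict the result. The analysis is secondary and declared unpowered, and splitting by phase does not make it powered. The reason to act is that the estimates are meant to inform the next trial's design. Whether the Experiment-phase ratio should become the lead estimate is a trade-off that the documents do not settle, given how few events that phase will hold.

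**What to change.** In section 4.18:

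1. Start the clock at randomization, and report run-in events descriptively.
2. State the censoring time for the first-event and recurrent-event models.
3. Keep the whole-period log-rank, Cox and Andersen-Gill comparisons.
4. Add an arm-by-phase term (Experiment, Observation, follow-up) to the Cox and Andersen-Gill models, and report phase-specific ratios with confidence intervals beside the overall ratio.
5. Optionally, add a sensitivity analysis whose event also includes dated oral steroid courses, which would recover some events.

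The cost is SAP wording and two extra terms per contrast. The visits are already abstracted with dates. The change should be written in before the statistics team is unblinded, so that the split does not look driven by the data.

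There are two downsides. Phase-specific intervals will be wide: about 20 to 23 first events in Arms 1 and 3 during the Experiment phase at a hazard ratio of 0.5, and fewer for Arm 1 versus Arm 2. First-event ratios in the later phases also condition on having had no earlier event, so they are no longer clean randomized comparisons. For those phases the recurrent-event model is preferable.

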4.14 Primary Endpoint

The primary outcome will be adherence to ICS regimen both during the *Experiment* interval (months 1-3). Adherence over these study intervals will be characterized as a daily observed-to-prescribed ICS adherence proportion averaged by study month. To operationalize this, a daily medication use log composed of 180 sequential ICS use observations will be generated, representing the count of ICS doses taken each day of study enrollment. These daily counts will be converted into proportions by dividing by the daily prescribed dose and imposing an upper limit of 1 in order to prevent doses taken above the prescribed limit – either during the use of flare plans or attempted “gaming” of the incentives by the participants – from influencing interval adherence estimates. Observed actuations will be quantified using electronic sensors.

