Secondary analysis: We will construct adherence trajectories for the combined *Experiment + Observation* interval for each study participant using group based trajectory modeling (GBTM). This modeling approach accounts for changing behavior over time and allows for identification of several distinctive developmental progressions without imposing the requirement that they vary normally about the population mean.^{21,22} Thus, participants with similar daily adherence trajectories are grouped about similar longitudinal trends and the model output is probabilistic assignment of each individual to one of several (up to six) adherence groups. Based on group-based modeling research on medication adherence from other conditions, anticipated ICS trajectory groupings will likely include: (1) severe early non-adherence, (2) severe delayed non-adherence, (3) moderate or episodic non-adherence, and (4) sustained adherence.^{23,24} (See Figure 3 for a preliminary 3-group ICS adherence trajectory model from our prior work.) Adherence group/category will then become the dependent variable for subsequent analysis in which a multinomial or ordered logistic regression will be applied with treatment arm as the exposure, adjusting for the covariates

[figure not shown]

Figure 3: 30-day post-discharge ICS adherence trajectories. (From Kenyon, et al. *J Asthma*. 2018.)

described above. For each adherence trajectory group, relative risk ratios for arms 1 and 2 compared to arm 3 will be calculated. We will test for overall effect of treatment arm on adherence trajectory in addition to important permutations (i.e. Arm 1 compared to Arm 3 within sustained adherence trajectory) using chi-square tests and generate marginal estimates of the probability of trajectory group membership, given treatment arm assignment (e.g. the probability of being in the sustained trajectory group if randomized to Arm 1 vs Arm 2 vs Arm 3). Findings presented alongside the primary analysis of observed-to-prescribed interval adherence percentage.

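### The trajectory model runs across the planned stop of all intervention components with no term for it, so a fast fall at withdrawal may be drawn partly as waning under incentives

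*Combined protocol and SAP*

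**What the plan says.** Section 4.16.2 (secondary analysis) constructs "adherence trajectories for the combined *Experiment + Observation* interval". It works at the daily level: "participants with similar daily adherence trajectories are grouped about similar longitudinal trends". Section 4.14 supplies the series: "a daily medication use log composed of 180 sequential ICS use observations will be generated".

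Section 4.18 (Aim 2) gives the functional form. Models with different numbers of groups are fitted "using quadratic trajectories (or possibly higher order polynomials") in PROC TRAJ and compared on BIC and minimum group size. It does not restate the time span, which comes from 4.16.2. Neither section names a breakpoint, spline, phase term or separate fit per phase, and neither fixes the polynomial order.

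Section 3.1.3 places a planned discontinuity in the middle of that span. "The financial incentives in Arm 1 will consist of 3 months of fixed-ratio incentives for each ICS actuation", and after the Experiment interval "all reminders, feedback, and incentives will cease". In the pilot (1.4), mean adherence was 80% in the intervention month, and "adherence dropped to 33% after incentives, reminders, and feedback ceased".

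The groups are then used further (4.16.2): "Adherence group/category will then become the dependent variable for subsequent analysis". They also serve the mediation analysis and the contrast of interview themes in 4.18.

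**The concern.** Whether adherence lasts once incentives end is the question that 1.4 leaves open, and the Observation phase exists to answer it. A low-order polynomial in time changes slowly from day to day. If a group of children holds steady for three months and then drops when support ends, a smooth curve has to begin falling before the drop and finish after it. The reader then sees waning during the incentive phase that did not happen, and the group may be named as a gradual or delayed decline.

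Loss caused by withdrawal and fading under incentives point to different designs for the multicenter study that 4.17 has in view. BIC cannot correct the shape if no candidate model allows a step.

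**Working it through.** The plan states no figure for the trajectory model, so there is none to reproduce. The check fits the planned curve to a known pattern.

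**Inputs.**
- 180 daily values (4.14).
- Withdrawal at day 90, derived as 3 months (3.1.3) × the 30-day interval used there for incentive payments.
- Levels 0.80 and 0.33 (1.4), a drop of 0.47.
- Polynomial order 2 as planned. Orders 3 to 5 are an assumption, because the plan sets no upper order.
- Length of the fall, L = 0, 14 or 30 days. This is an assumption, because the documents do not give the speed.

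**Pattern.** y(d) = 0.80 for d ≤ 90; y(d) = 0.80 − 0.47(d − 90)/L for 90 < d ≤ 90 + L; y(d) = 0.33 afterwards. Each polynomial is fitted by least squares. The error is the fitted minus the true monthly mean.

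**Quadratic, instantaneous step, by hand.** Put t = d − 90.5. The step is antisymmetric about t = 0, so the squared term is zero and the best quadratic is a straight line.
- Σ|t| = 8,100 and Σt² = 180 × (180² − 1)/12 = 485,985.
- Slope = −0.235 × 8,100 / 485,985 = −0.00392 per day. The mean is 0.565.
- Month centres are t = −75, −45, −15, 15, 45, 75, so the fitted month means are 0.86, 0.74, 0.62, 0.51, 0.39, 0.27. The truth is 0.80 three times, then 0.33 three times.
- Month 3 error: 0.62 − 0.80 = −0.18. Month 4 error: 0.51 − 0.33 = +0.18.
- Day 1 is 0.92 and day 90 is 0.57. That is a false fall of 0.35, or 74% of the true drop, inside a flat phase. On the logit scale the curve runs from 0.89 to 0.57.

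**Month 3 error in percentage points, by order and speed of fall:**

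| Order | L = 0 | L = 14 days | L = 30 days |
|---|---|---|---|
| 2 | −18 | −14 | −10 |
| 3 | −13 | −10 | −6 |
| 4 | −13 | −8 | −4 |
| 5 | −9 | −5 | −2 |

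**Ambiguity.** A truly gradual linear decline from 0.80 to 0.33 over 180 days also gives a quadratic value of 0.57 on day 90, the same as the step.

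**Fit with a phase term.** A normal-mixture trajectory model with 2 to 5 groups was fitted to three simulated trials of 125 with an assumed mix of patterns. BIC (higher is better) was 1779, 1108, 1495 for quadratics; 2365, 1650, 2079 for quintics; and 2838, 2064, 2476 for a step at day 90. The step's gain over the quintic is 473, 414 and 397. In four further simulated trials that mixed step children and gradual decliners, the gain over the quintic was about 85 to 117.

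**Group membership.** The simulations disagree.
- In the first three trials, every child placed in the step group was a true step child under every model.
- In three other trials, each with 30 gradual decliners whose slope was set to the quadratic's own fit (the hardest case), all 30 shared groups with step children under quadratics. Under quintics 10, 11 and 30 did, and with a phase term 9, 4 and 0 did.
- In the four further trials, the phase term clearly improved assignment in only one.

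**The case against.** A reader might infer that the plan will present a withdrawal effect as waning, and that the error passes into the arm comparison, the mediation analysis and the interview analysis. The documents do not support that, for four reasons.

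1. Section 1.4 gives interval averages from a 30-day pilot. It does not say how fast adherence fell, or that the same fall follows three months of incentives. The 18-point error is the worst case in the table: an instantaneous drop with the lowest order.
2. Section 4.18 permits higher orders. In the simulations BIC strongly preferred a quintic to a quadratic, and with a 30-day fall the quintic's month 3 error is only 2 points.
3. The later analyses use group membership, not the fitted curve. The interviews are first split into sustained and non-sustained, and a child falling from 80% to 33% would be non-sustained however the curve bends.
4. Persistence is analysed separately. Observation-phase adherence is its own secondary endpoint (4.15), and the GEE in 4.16.2 has arm-by-month terms. If month is categorical, which 4.16.2 does not say, the fall from month 3 to month 4 appears directly. The trajectory findings are to be reported beside the interval adherence.

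All four stand, and they limit the point to the shape and labelling of the curves. They do not remove it. Higher orders are optional, none of those tested reproduces a fast fall, and a model that allows a step cannot be selected if it is never a candidate. That a phase term reproduces a pure step is true by construction and is not evidence in itself.

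**Conclusion.** The concern holds in a limited form. The trajectory model spans a known stop of every component with no means of representing it. If the fall at withdrawal is fast, the fitted curves may move part of it into the incentive phase and so may mislabel groups. Month 3 adherence would be understated by 9 to 18 points for an instantaneous fall of the pilot's size, and by 2 to 10 points if the fall takes 30 days, depending on the order chosen. These figures rest on a flat 0.80 before day 90, a flat 0.33 after the fall, and orders 2 to 5. With a truly gradual decline there is no distortion.

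The primary analysis is untouched. A change in group membership depends on the mix of patterns among the children and is not established, so no bias in the arm, mediation or interview results should be claimed. The change is still worth making before the groups are fitted, because it is cheap and bears on the question that the Observation phase was added to answer.

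**What to change.** In 4.16.2 and 4.18, add two forms to the candidate PROC TRAJ models: a phase indicator switching at the end of month 3, entered as a time-varying covariate, and separate polynomials before and after that point. Compare both by BIC with the smooth polynomials already planned, and state the highest order that will be tried. Plot observed weekly or monthly group means over each fitted curve, so that a poor fit at withdrawal is visible whichever model is chosen.

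Both forms are worth listing. Separate polynomials fit days 1 to 90 on their own, so a flat incentive phase stays flat whatever the speed of the later fall. A quadratic plus indicator is cheaper but suits only an abrupt fall: fitted to the 30-day pattern above, it leaves errors of −2 points in month 3, −5 in month 4 and +9 in month 5.

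The cost is a few lines of SAP text, one extra parameter per group for the indicator or several for separate polynomials, and no new data.
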